Hypothesis: MRI-guided treatment planning and delivery can **selectively target high-risk prostate nodules and deliver a higher radiation dose, to achieve maximal local control without increasing treatment toxicity**

Primary objective: **To assess feasibility and safety of delivering MRI-guided prostate SBRT with a simultaneous integrated boost to MRI-visible lesions.**

[figure not shown]
Feasibility is defined as a plan meeting treatment planning objectives and normal tissue constraints. Specifically the dose distribution of the MRI-guided technique, will be assessed with regard to fulfilling protocol requirements of: a) coverage of the planning target volume (PTV) , b) constraints to organs at risk (OAR) by dose volume histogram (DVH) analysis and whether this can be done through standard set-up techniques or non-invasively through MRI based planning, c) coverage of high-risk prostate nodules. The total dose (either 37.5, 40, 42.5 or 45 Gy) will be determined by selecting the plan that delivers the highest dose to contoured visible nodules while maintaining normal tissue constraints to the urethra and rectum. We will track the number of treatment plans for each dose level (37.5, 40, 42.5 or 45 Gy) that can be delivered while meeting radiation planning objectives.

Safety of this approach will be determined by assessing acute GI/GU toxicity (CTCAE 4.0 criteria). Treatment will be deemed safe if there is no acute >G3 GI/GU toxicity within the first 30 days of treatment (CTCAE 4.0 criteria). Given that the treatment plans will meet rigorous normal tissue constraints used for standard prostate SBRT, we do not anticipate any increased toxicity on this study compared to standard prostate SBRT.

Secondary objectives:

1. To obtain health-related quality of life (HRQOL) measured using: 1) the Expanded Prostate Cancer Index Composite (EPIC) short form questionnaire, 2) AUA. Assessment will occur at baseline, and at first follow up.

SCHEMA

Blood samples for immune monitoring studies and stool samples for microbiome studies will be collected at baseline, end of Radiation at 3-6 months post follow up visit.

TABLE OF CONTENTS

| | |
|--|-----------|
| PROTOCOL SUMMARY | 9 |
| SCHEMA..... | 11 |
| 1 STUDY OBJECTIVES | 14 |
| 1.1 PRIMARY OBJECTIVES | 14 |
| 1.2 SECONDARY OBJECTIVES | 14 |
| 2 BACKGROUND | 14 |
| 2.1 PROSTATE CANCER RADIOTHERAPY..... | 14 |
| 2.2 BIOLOGICAL RATIONALE FOR SBRT | 15 |
| 2.3 SBRT OUTCOMES..... | 16 |

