1.1 Primary Objectives

1.1.1 Determine the feasibility and safety of delivering SBRT w/SIB without increased acute G3 GI/GU toxicity.

Feasibility is defined as a plan meeting treatment planning objectives and normal tissue constraints. Specifically the dose distribution of the MRI-guided technique, will be assessed with regard to fulfilling protocol requirements of: a) coverage of the planning target volume (PTV) , b) constraints to organs at risk (OAR) by dose volume histogram (DVH) analysis and whether this can be done through standard set-up techniques or non-invasively through MRI based planning, c) coverage of high-risk prostate nodules. The total dose delivered (either 37.5, 40, 42.5 or 45 Gy mean dose to the contoured nodule) will be determined by selecting the plan with the highest dose to visible nodules while maintaining normal tissue constraints to the urethra and rectum. We will track the number of treatment plans for each dose level (37.5, 40, 42.5 or 45 Gy) that can be delivered while planning objectives.

Safety of this approach will be determined by assessing acute GI/GU toxicity (CTCAE 4.0 criteria). Treatment will be deemed safe if there is no acute >G3 GI/GU toxicity within the first 30 days of treatment (CTCAE 4.0 criteria). Given that the treatment plans will meet standard normal tissue constraints used for prostate SBRT, we do not anticipate any increased toxicity on this study compared to standard prostate SBRT.

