2.6 ViewRay: a unique radiation delivery approach

The ViewRay MRIdian Linac system is a radiation delivery machine that integrates a linear accelerator with real-time MRI imaging. The ViewRay machine allows fusion of MR imaging with treatment planning. The uniqueness of this approach is the image guided delivery component, based on precise MRI-based detection of target and normal tissue during treatment in real-time. The ViewRay will provide real-time MRI imaging to ensure that the high-dose region is precisely targeted. MRI guided radiation has the benefit of not requiring fiducial implantation or excess radiation exposure from multiple cone beam CT. Furthermore, motion monitoring can be

performed with images acquired up to 4 frames a second, allowing live feedback of treatment position.

ViewRay offers the ideal system for delivery of prostate SBRT, due to its ability to provide image guidance “live”, during treatment. Real-time MRI imaging allows superior soft-tissue differentiation with excellent visualization of the prostate. This ViewRay platform offers the ideal setting for this study, that aims at precisely delivering prostate SBRT with a simultaneous integrated boost to visible nodules.

The goal of this study is to assess feasibility and safety of using the ViewRay to deliver prostate SBRT with SIB. Feasibility is defined as the ability to deliver treatment as planned (within the constraints defined in Section 5.3 Radiation Planning) and safety is defined as lack of acute G3 GI or GU toxicity within 30 days. The proposed SBRT dose (35-36.25 Gy in 5 fractions to the whole prostate) has been reported in the literature to be safe and well tolerated (Table 2), with no acute G3 toxicity. The proposed boost dose of an additional 0.5, 1.0, 1.5 or 2 Gy per fraction (total dose 37.5-45 Gy, depending on normal tissue constraints) is within the range of current standard of care SBRT doses, and is expected to be well-tolerated if normal tissue constraints are met. By applying rigorous normal tissue constraints and capitalizing on the imaging capability of the ViewRay we plan to deliver a treatment that is non-invasive and exceptionally precise.

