5 STUDY PROCEDURES

| | Pre-Study | Fx 1 | Fx2 | Fx 3 | Fx 4 | Fx 5* | Post-RT Visit (3-6 month s/p RT) |
|--|-----------|------|-----|------|------|-------|----------------------------------|
| Informed consent | X | | | | | | |
| Demographics | X | | | | | | |
| PSA | X | | | | | | X |
| Acute/Late Toxicity Assessment (CTCAE) | X | | | | | X | X |
| EPIC-26, AUA | X | | | | | | X |
| Imaging: Planning CT/MR; | X | | | | | | |
| Optional: blood draw and microbiome sample | X | | | | | X | X |

**at physician's discretion, lymph nodes may be targeted in the radiation field, either in 5 fractions or over 5-6 weeks using standard fractionation*

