7 ADVERSE EVENT REPORTING REQUIREMENTS

Adverse event (AE) monitoring and reporting is a routine part of every clinical trial. The investigator will be required to provide appropriate information concerning any findings that suggest significant hazards, contraindications, side effects, or precautions pertinent to the safe use of the drug or device under investigation. Safety will be monitored by evaluation of adverse events reported by patients or observed by investigators or research staff, as well as by other investigations such as clinical laboratory tests, x-rays, electrocardiographs, etc.

7.1 *Adverse Event Definition*

An adverse event (also referred to as an adverse experience) can be any unfavorable and unintended sign (e.g., an abnormal laboratory finding), symptom, or disease temporally associated with treatment, and does not imply any judgment about causality.

Adverse Event Characteristics and Related Attributions

CTCAE term (AE description) and grade: The descriptions and grading scales found in the revised NCI Common Terminology Criteria for Adverse Events (CTCAE) version 4.0 will be utilized for grade 3 or higher AE reporting. A copy of the CTCAE version 4.0 can be downloaded from the CTEP web site (<http://ctep.cancer.gov>).

- **Attribution** of the AE:

- Definite – The AE is *clearly related* to the study treatment.
- Probable – The AE is *likely related* to the study treatment.
- Possible – The AE *may be related* to the study treatment.
- Unlikely – The AE is *doubtfully related* to the study treatment.
- Unrelated – The AE is *clearly NOT related* to the study treatment.

7.2 *Recording of Adverse Events*

All adverse events will be recorded on a patient specific AE log. The AE log will be maintained by the research staff and kept in the patient's research chart.

7.2.1 **Reporting of AE to WCMC IRB**

All AEs occurring on this study will be reported to the IRB according to the IRB policy, which can be accessed via the following link:

http://researchintegrity.weill.cornell.edu/forms_and_policies/forms/Immediate_Reportin...

7.3 *Definition of SAE*

SAE's include death, life threatening adverse experiences, hospitalization or prolongation of hospitalization, disability or incapacitation, overdose, congenital anomalies and any other serious events that may jeopardize the subject or require medical or surgical intervention to prevent one of the outcomes listed in this definition.

7.3.1 *Reporting of SAE to IRB*

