10 MEASUREMENT OF EFFECT

This is a feasibility study. Feasibility will be achieved if a treatment plan can be achieved with the parameters described below:

Specifically the treatment must fulfill all three aspects of a) coverage of the prostate PTV as defined in 5.3 to dose of 35 Gy in 5 fractions, b) no more than acceptable radiation dosage to organs at risk (OAR) by DVH analysis (refer to section 5.3), and c) full coverage of high-risk prostate nodules, as defined by mean dose to contoured nodules. The total mean dose to be delivered (either 37.5, 40, 42.5 or 45 Gy) will be determined by selecting the plan with the highest dose to visible nodules while maintaining normal tissue constraints. The first primary endpoint will be degree of feasibility, as measured by the percentage of treatments that are delivered according to plan.

Safety of this approach will be determined by assessing acute GI/GU toxicity (CTCAE 4.0 criteria). Treatment will be deemed safe if there are no acute greater than grade 3 GI/GU adverse events within the first 30 days of treatment (CTCAE 4.0 criteria). The second primary endpoint will be safety, as measured by the percentage of treatments that are delivered without GI/GU toxicity within the first 30 days from start of treatment. Given that the treatment plans will meet standard normal

tissue constraints used for SBRT, and rigorous safety metrics need to be met before radiation is delivered, we do not anticipate any increased toxicity on this study compared to standard SBRT.

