12.4 Analysis of Primary and Secondary Endpoints

Primary Endpoint:

The first primary endpoint of feasibility will be measured by the percentage of treatments that are delivered according to plan. The count and percent will be tabulated, and a 95% confidence interval estimated using an exact Clopper-Pearson binomial two-sided interval.

The second primary endpoint of safety will be measured by the percentage of treatments that do not lead to a GI/GU adverse event (defined as >Grade 3) within 30 days of treatment. The count and percent will be similarly tabulated, and a 95% confidence interval estimated using an exact Clopper-Pearson binomial two-sided interval.

Finally, the proportion of patients for whom the treatment was feasible and safe will be tabulated, and a 95% confidence interval estimated using an exact Clopper-Pearson binomial two-sided interval.

Planned sub-group analyses include feasibility, safety, and combination of both within each of the four potential target dose levels (37.5, 40, 42.5 or 45 Gy).

Secondary Endpoints:

HRQOL measures at baseline and at follow up (3-6 months post treatment start) will be summarized numerically and graphically using mean (sd), median (interquartile range), or count (percent) as appropriate, and 95% confidence intervals estimated where possible. Changes in scoring from pre- to post-treatment will also be similarly studied. EPIC overall scores as well as domain summary scores (urinary incontinence, urinary irritative/obstructive, bowel, sexual, hormonal) and individual item responses will be studied. Similarly, overall score as well as individual item responses will be studied for the AUA symptom survey.

13 Data and Safety Monitoring Plan (DSMP)

The WCMC Data and Safety Monitoring Committee (DSMC) is the central monitoring board for this study.

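### The primary safety endpoint has two thresholds: the objective and Section 2.6 refer to acute Grade 3, while the decision rule and analysis count only events above Grade 3

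*Combined protocol and SAP*

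**What the plan says.** The document describes the second primary endpoint, safety, in three ways.

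- **Grade 3.** The primary objective, stated in 1.1.1 and repeated in 12.1.1, is delivery "without increased acute G3 GI/GU toxicity". Section 2.6 gives an explicit definition: "safety is defined as lack of acute G3 GI or GU toxicity within 30 days".
- **Above Grade 3.** The decision rule in the Protocol Summary and 1.1.1 reads: "Treatment will be deemed safe if there is no acute >G3 GI/GU toxicity within the first 30 days of treatment". Section 10 puts the same rule in words: "no acute greater than grade 3 GI/GU adverse events within the first 30 days of treatment". The endpoint in 12.1.1 also uses the higher threshold in words, and 12.4 analyses the "percentage of treatments that do not lead to a GI/GU adverse event (defined as >Grade 3) within 30 days of treatment".
- **No grade.** The endpoint sentence in Section 10 reads "percentage of treatments that are delivered without GI/GU toxicity within the first 30 days from start of treatment".

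Two other sections bear on the matter. In 7.1, CTCAE version 4.0 "will be utilized for grade 3 or higher AE reporting". The stopping rule in 13.2 is triggered by events of Grade 4 or higher.

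Section 12.4 also plans a combined feasible-and-safe proportion, and feasibility, safety and their combination within each of the four boost dose levels. All of these inherit the safety definition.

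**The concern.** An acute Grade 3 GI or GU event is the outcome the objective names. Under 12.4 that event is scored as a success. Grade 3 events would still be recorded and reported as adverse events, but they would not enter the primary safety percentage or its confidence interval. The stated objective would then have no primary estimate.

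If Grade 3 events occur and no Grade 4 or 5 event does, the same data meet the rule for declaring treatment safe and fail the Section 2.6 definition. With the conflict unresolved, the threshold could be chosen after the data are seen. A cluster of Grade 3 events at a higher boost level would also not show in that subgroup's safety percentage.

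**Working it through.** **Could the conflict be a lost symbol?** A greater-than-or-equal sign read as a plain greater-than sign would explain the symbol in the Summary, 1.1.1 and 12.4. It would not explain Sections 10 and 12.1.1, which state the higher threshold in words. No section says that the symbol is meant to include Grade 3.

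**How one patient is classified** (worst acute GI/GU event within 30 days):

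| Worst grade | Section 2.6 | Decision rule, 12.1.1, 12.4 | Section 10 endpoint sentence, read literally |
|---|---|---|---|
| 1 or 2 | safe | safe | not safe |
| 3 | not safe | **safe** | not safe |
| 4 or 5 | not safe | not safe | not safe |

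Section 2.6 is read here as Grade 3 or higher. The last column is probably a dropped qualifier, because an earlier sentence in the same Section 10 paragraph carries the grade.

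**Inputs.** n = 30 and the exact two-sided 95% Clopper-Pearson interval (12.2, 12.4). The numbers of Grade 3 events below are assumptions for illustration.

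**Formula.** For x successes in n, the lower limit is the 0.025 quantile of Beta(x, n − x + 1) and the upper limit is the 0.975 quantile of Beta(x + 1, n − x). When x = n, the lower limit is 0.025^(1/n) and the upper limit is 1.

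**The plan's own figure.** For 15/30 the formula gives 31.3% to 68.7%, as stated in 12.2. (The half-width is (68.7 − 31.3)/2 = 18.7 points, not the 16 stated beside it. That is a separate matter.) The plan gives no corresponding figure for safety.

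**Safety under each definition, no Grade 4 or 5 events:**

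| Patients with acute Grade 3 | Section 12.4 | Section 2.6 |
|---|---|---|
| 1 of 30 | 30/30 = 100% (88.4 to 100) | 29/30 = 96.7% (82.8 to 99.9) |
| 2 of 30 | 30/30 = 100% (88.4 to 100) | 28/30 = 93.3% (77.9 to 99.2) |
| 4 of 30 | 30/30 = 100% (88.4 to 100) | 26/30 = 86.7% (69.3 to 96.2) |
| 2 of 8 in one dose level (assumed size) | 8/8 = 100% (63.1 to 100) | 6/8 = 75.0% (34.9 to 96.8) |

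Check: 0.025^(1/30) = 0.884 and 0.025^(1/8) = 0.631.

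**How likely are opposite verdicts?** They arise whenever at least one Grade 3 event occurs and no Grade 4 or 5 event does. The chance of at least one Grade 3 event in 30 is 1 − (1 − p)^30:

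- p = 1%: 1 − 0.99^30 = 26%
- p = 3%: 1 − 0.97^30 = 60%
- p = 5%: 1 − 0.95^30 = 79%

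These rates are assumptions. The only acute figure in the document is the remark in 2.6 that no acute Grade 3 toxicity was reported at the whole-prostate dose. No acute rate is given for boosted treatment.

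**The case against.** The strongest reply is that the operative text is consistent. The decision rule, the 12.1.1 endpoint and the 12.4 analysis all use the higher threshold, and the stopping rule matches it numerically. The only contrary definition is one sentence in the Background. The objective's wording is comparative and is not an event definition, and the Summary's version of the objective names no grade. A statistician following Section 12 has one rule to execute.

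Part of this stands. Grade 4 or higher may well be intended, and then 12.4 is right and the objective and Section 2.6 are wrong. But a stopping rule does not define an endpoint, and the objective names Grade 3 in the statistical section itself. The text needs amending on either reading.

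Other points that stand:

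- The larger illustrative counts are high. 4/30 = 13.3% exceeds the largest single-site figures in Table 2 (GI 4.4%, GU 3.5%), which the text treats as late toxicity. The conflict does not depend on them: one Grade 3 event is enough to split the verdict.
- This is a 30-patient single-arm study with no safety test and no reference rate. A Grade 3 or higher estimate describes toxicity and cannot by itself show whether it is increased.
- All adverse events are logged, so Grade 3 counts could be tabulated later. That limits the loss of information. It does not settle which definition decides whether treatment is declared safe.

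**Conclusion.** The concern holds. One of the two primary endpoints is defined at incompatible thresholds, no section reconciles them, and the analysed version scores the event named in the objective as a success. Under 12.4 the safety result is 100% (88.4 to 100) however many acute Grade 3 events occur, provided there is no Grade 4 or 5 event. Counting Grade 3 gives 96.7% with one such event and 93.3% with two, and the Section 2.6 definition fails in both cases.

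The contradiction rests on the text alone. Its numerical size rests on assumed event counts and rates and on an assumed subgroup of 8. The documents do not settle which threshold was intended. Because this determines what counts as an event in a primary endpoint, it must be resolved before analysis.

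**What to change.** Choose one threshold and use it in the Summary, 1.1.1, 2.6, 10, 12.1.1 and 12.4, including the combined proportion and the dose-level subgroups. State the grade in the Section 10 endpoint sentence.

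- **If the Grade 3 objective stands,** analyse Grade 3 or higher in 12.4 with its exact interval and tabulate Grade 4 or higher separately.
- **If Grade 4 or higher is intended,** remove the Grade 3 claim from the objective and Section 2.6. Still report the Grade 3 or higher proportion with its exact interval, since that is the level Table 2 and the adverse event reporting use.

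The cost is a wording amendment and one extra table. If Grade 3 or higher is chosen, the safety percentage may fall and the zero-event rule becomes harder to meet: at assumed true rates of 1%, 3% and 5%, it would fail with probability 26%, 60% and 79%.

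Ascertainment limits either choice. CTCAE assessment is scheduled at pre-study, fraction 5 and 3 to 6 months. With the 2 to 3 week course expected in 5.5, fraction 5 falls at about day 14 to 21. That leaves 30 − 21 = 9 to 30 − 14 = 16 days of a window counted from treatment start without a scheduled assessment. The gap nearly closes if fractions are given weekly, which 5.5 allows. Events in the gap would rely on the adverse event log, so the amendment should say how they are to be captured for the endpoint.

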13.1 Monitoring plan

This study will be conducted in accordance with the guidelines in the 2001 NCI approved data Safety and Monitoring plan for the WCMC Cancer Institute Monitoring will occur on a yearly basis from the date the first patient is enrolled. Reports to the Data Safety and Monitoring Committee will include the following information: accruals, targets, responses, adverse events and evidence of reporting to appropriate review committees. The WCMC Data and Safety Monitoring Board (DSMB) will review the IRB approved protocol, the data and safety monitoring plan and any stopping guidelines during protocol initiation. During the course of the study, the DSMB will review cumulative study data twice a year to evaluate safety, efficacy, study conduct, and scientific validity and integrity of the trial. The WCMC DSMB may also convene as needed if stopping criteria are met or other safety issues arise that the Principal Investigator and/or IRB would like the WCMC DSMB to address.

13.2 Stopping rules

If patients experience more than one grade 4 or higher toxicity within one month of RT, the study will not proceed further.

